7.5.3 Current Status of PFS and OS Follow-Up

The extent of follow-up for survival, defined as the time between randomization date and last known date alive (for patients who are alive) or death date (for patients who died), will be summarized descriptively (median, minimum, maximum) in months for all randomized patients.

The currentness of follow-up for survival, defined as the time between last OS contact (i.e., last known alive date or death date) and clinical data cutoff date, will be summarized in months for

all randomized patients. Patients who died and patients with last known alive date on or after data cutoff date will have zero value for currentness of follow-up.

The currentness of follow-up for PFS, defined as time from last evaluable tumor assessment to cutoff date will be summarized by treatment group and overall for all randomized patients. Patients who have a PFS event will be considered as current for this analysis.

The currentness of follow-up will be categorized into the following categories: 0 month, 0-3 months, 3-6 months, 6-9 months, 9-12 months, and 12 or more months.

In addition, time to treatment discontinuation will be summarized and presented by treatment group using a Kaplan-Meier curve whereby the last dose date will be the event date for those patients who are off study therapy. Median duration of study therapy and associated 95% CI will be provided. Patients who are still on study therapy will be censored on their last dose date. Time to NKTR-214 discontinuation will be summarized in the same way as well.

7.5.4 Efficacy Analysis of Other Endpoints

7.5.4.1 Progression-Free Survival 2

PFS on next-line therapy (PFS2) is defined as the time from randomization to documented progression, per investigator assessment, after the next line of therapy or to death from any cause, whichever occurs first. Patients who were alive and without progression after the next line of therapy will be censored at last known alive date. The following censoring rules will be applied for PFS2:

For a patient who did not receive subsequent anti-cancer therapy:

- If the patient died, the patient is considered as an event on the date of death
- Else, the patient is censored at his/her last known alive date

For a patient who received subsequent anti-cancer therapy:

- If the patient had disease progression after the start of subsequent anti-cancer therapy, the patient is considered as an event on the date of PD
- Else if the patient died or started a second subsequent anti-cancer therapy, the patient is considered as an event at the death date or at the start date of second subsequent therapy whichever is the earliest.
- Else, the patient is censored at his/her last known alive date

PFS2 will be analyzed as follows:

- The PFS2 will be compared between treatment arms using a two-sided logrank test, stratified by the stratification factors for analysis (IMDC prognostic score and TKI choice) as defined in Section 6.5. The HR for PFS2 with its corresponding two-sided 95% CI will also be provided, estimated via a stratified Cox model with the stratifications factors specified above and treatment arm as the only covariate in the model.
- The Kaplan-Meier method will be used to further summarize PFS2, including Kaplan-Meier curves, and medians with corresponding 95% CIs.

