EQ-5D-3L	X		X	X	X	Patients should complete the assessment at the start of the clinic visit, prior to dosing and scheduled activities.
FKSI-19	X		X	X	X	
PRO-CTCAE	X		X	X	X	Completed on Days 1 and 22 of every cycle through Cycle 4, and then on Day 1 of the following cycles. See Section 7.6 for further details.

Abbreviations used in this table appear on the final page of [Table 4](#).

Table 3: On-Treatment Schedule of Events for Arm B (Contd)

Procedure ^a	Arm B Cabozantinib 60 mg PO once daily (continuously) OR Sunitinib 50 mg PO once daily (4 weeks on treatment, followed by 2 weeks off treatment) Cycle = 6 Weeks					Notes
	Cycle 1			Cycle 2 and subsequent on-treatment visits		
	Day 1	Day 8 (-1 day)	Day 22 (± 3 days)	Day 1 (± 3 days)	Day 22 (± 3 days)	
Health Care Resource Utilization	X		X	X	X	Site staff will collect the health care resource utilization data at each visit using the CRF.

a. Assessments and visits that occur outside of protocol-specified windows (e.g., for holidays, travel issues, insurance issues) may be acceptable on a case-by-case basis after review by the Medical Monitor.

Abbreviations used in this table appear on the final page of [Table 4](#).

Table 4: Long-Term Follow-Up Schedule of Events

Procedure ^a	Safety Follow-Up Visit 1 ^b	Safety Follow-Up Visit 2 ^b	Survival Follow-Up ^c Every 12 Weeks (± 14 days)	Notes ^d
Safety Assessments				
Vital Signs	X	X		Blood pressure, heart rate, temperature Weight
AE and SAE Assessments	X	X	X	All AEs will be documented until 100 days after the last dose of all study drug(s). SAEs to be collected after the 100-day safety visit if the SAE is deemed to be related or residual toxicities are persisting. Patients will be followed for drug-related toxicities until these toxicities resolve, return to baseline, or are deemed irreversible.
Karnofsky Performance Status	X	X		See Appendix 2 .
Review of Subsequent Medications and Anticancer Therapy	X	X	X	In Survival Follow-up, subsequent anticancer treatment only. Additional subsequent anticancer therapy details such as regimen, setting of the regimen, line of therapy, start date and end date of each regimen, best response to the regimen, and date of progression to subsequent anticancer therapies will be collected.
Laboratory Tests				
Pregnancy Test (WOCBP only)	X	X		Patients (WOCBP) will continue to follow instructions for methods of contraception through 5 months post treatment completion.

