Duration of Response	
Duration of response (DOR) is defined for patients who have a confirmed CR or PR as the date from first documented CR or PR per mRECIST 1.1 to the date of the documentation of disease progression as assessed by BICR or death due to any cause, whichever is earlier. The same censoring method used for the primary PFS analysis will be applied. The median DOR will be estimated using the Kaplan-Meier method with corresponding 95% CI and range.
 
The duration of overall complete response is measured from the time measurement criteria are first met for CR until the first date that recurrent disease is objectively documented.
 
Time to response (TTR) is defined for patients who had a confirmed CR or PR as the time from the date of randomization to date of first documented CR or PR per mRECIST 1.1 as assessed by BICR. The median TTR will be estimated using the Kaplan-Meier method with corresponding 95% CI and range.
 
The clinical benefit rate (CBR), defined as the number of patients with CR, PR, or SD per mRECIST 1.1 by BICR, will be summarized similarly to ORR. Note that a best overall response of SD requires a minimum of 56 days on study from randomization to date of the first tumor assessment.
 
ORR, DOR, TTR, and CBR assessed by Investigator per mRECIST 1.1 will be analyzed similarly to these endpoints assessed by BICR. ORR, DOR, TTR, and CBR assessed by Investigator per mRECIST 1.1 will be analyzed similarly to these endpoints assessed by BICR.

PFS2	
PFS after the next line of treatment (PFS2) is defined as time from randomization to progression per Investigator after the start of next line of therapy or death, whichever occurs first. Patients who were alive and without progression after the next line of therapy will be censored at their last known alive date. Details on PFS2 analysis will be described in the SAP.

FKSI-19	
Summary statistics for FKSI-19 score (and its 4 subscales) at each assessment point will be summarized for each treatment group. The mean change from baseline will also be reported at each post baseline assessment point.

EQ-5D-3L	
Summary statistics for EQ-5D-3L (5 dimensions) at each assessment point will be summarized for each treatment group. The mean change from baseline will also be reported at each post baseline assessment point.

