4.3 Other Efficacy Endpoints

- PFS2 (PFS after the next line of treatment), defined as time from randomization to objectively documented progression, per investigator assessment, after the next line of therapy or to death from any cause, whichever occurs first.
- Duration of response (DOR), defined as the time between the date of first confirmed documented response (CR or PR) to the date of the first documented tumor progression as determined per mRECIST 1.1 by the BICR, or death due to any cause, whichever occurs first.
- Time to response (TTR), defined as the time from randomization to the date of the first confirmed documented response (CR or PR) per mRECIST 1.1 by BICR.
- Clinical benefit rate (CBR), defined as defined as the number of patients with CR, PR, or SD per mRECIST 1.1 by BICR

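### The PFS2 rule counts the start of a second subsequent therapy as an event only if no progression is ever recorded after the first subsequent therapy starts, so the event date depends on later follow-up

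*SAP*

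**What the plan says.** The PFS2 definitions name two kinds of event. SAP 4.3 starts the clock at randomization and stops it at documented progression, "per investigator assessment, after the next line of therapy or to death from any cause, whichever occurs first". Protocol 9.5 has "progression per Investigator after the start of next line of therapy or death, whichever occurs first" and leaves the details to the SAP. The opening of SAP 7.5.4.1 likewise names only progression and death.

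The rules that follow in SAP 7.5.4.1 add a third kind of event. For a patient with subsequent therapy they run in order:

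- First step: "If the patient had disease progression after the start of subsequent anti-cancer therapy, the patient is considered as an event". The event takes the progression date.
- Second step, reached only if the first does not apply: "Else if the patient died or started a second subsequent anti-cancer therapy". The event is then dated at the earlier of those two, death or second therapy.
- Otherwise the patient is censored at the last known alive date.

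The arms are then compared with a stratified logrank test and a stratified Cox hazard ratio.

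**The concern.** The first step has no upper limit: it does not require the progression to come before a second subsequent therapy. The comparison of dates in the second step is between death and the second therapy only; progression is not part of it. A progression on a later line therefore displaces a therapy start that the same rule would otherwise have counted as the event.

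Whether a patient's event falls at the switch or later is then decided by what happens after the switch. A time-to-event rule should not work that way. An event already counted at one data cutoff can be redated later at the next. PFS2 is compared formally between arms, uses investigator-assessed progression, and sits in an open-label trial, so a difference between arms in switching without documented progression could carry through to the estimate.

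**Working it through.** There is no planned figure to reproduce, since no sample size, alpha or event count is involved. The check applies the rules to assumed timelines.

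**Inputs.** The event steps are those of SAP 7.5.4.1. The headline definitions are those of SAP 4.3, the opening of SAP 7.5.4.1 and protocol 9.5. All dates are assumed, in months from randomization: first subsequent therapy at 8, second at 14. Where there is more than one progression, the first is used. That reading is the most favourable to the SAP, whose text does not say *first*.

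**Rules compared.**

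- SAP steps: if any progression after 8, its date; else min(death, second therapy start); else censor.
- Headline definition: min(progression after 8, death); else censor.
- Earliest of three: min(progression after 8, second therapy start, death); else censor.

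| Patient | SAP steps | Headline definition | Earliest of three |
|---|---|---|---|
| A: progression at 13 and again at 20 | 13 | 13 | 13 |
| B: no progression on first subsequent line, progression at 20 | **20** | 20 | 14 |
| C: as B, but no later progression, alive at 24 | 14 | censored at 24 | 14 |
| D: as C, but death at 20 | 14 | 20 | 14 |
| B seen at a month-18 cutoff | **14** | censored at 18 | 14 |

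**Results.**

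1. B, C and D are identical through month 14. The SAP steps date C and D at 14 and B at 20, a gap of 20 − 14 = 6 months that follows only from the assumed dates.
2. B has an event at 14 at the month-18 cutoff and an event at 20 once the later progression is recorded. Under each of the other two rules no event already counted is redated.
3. The SAP steps agree with the headline definition for B but not for C or D, and with the earliest-of-three rule for C and D but not for B. They follow neither consistently.
4. A shows the limit of the problem: if progression on the first subsequent line is recorded, the rule already gives the earlier date.

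**Can a later-line progression reach the first step?** The notes to the Long-Term Follow-Up table in protocol 1.2 say "best response to the regimen, and date of progression to subsequent anticancer therapies will be collected", in the plural. Protocol 5.6.2 describes the progression date in the singular, after the next line. Neither place restricts which progression enters the PFS2 derivation.

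**Does the SAP set such a limit elsewhere?** Yes. In Table 3 (PFS), progression and death count only if no subsequent therapy came before. In SAP 7.5.1.1, best overall response stops at progression or subsequent therapy, whichever is first. The PFS2 steps have no counterpart.

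**The case against.** The strongest reply is that nothing is displaced. All the headline definitions name only progression and death, so for patient B month 20 is the event, and the second-therapy start is a substitute for use when no progression is documented. This has force. A reader might infer that the rule overwrites the *true* PFS2 event at month 14, and the documents do not support that: the second-therapy start becomes an event only through the second step. But the reply does not make the rule coherent. If the start is only a substitute, it is applied to C and D on the strength of what they did not do later, and for D it overrides a recorded death that the headline definition would use.

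A second reply is that the first step means progression on the first subsequent line, because the endpoint is described as relating to the next line and the second step speaks separately of a second subsequent therapy. That reading is possible and would date B at 14. It is not written, and a programmer following the text would not apply it.

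It is also fair that the affected group is narrow. A patient must have a first subsequent therapy, no recorded progression on it, a second subsequent therapy, and a recorded progression afterwards. Such a patient is an event under every rule considered; only the date moves.

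**Conclusion.** The rule is wrong as written: its event dates are internally inconsistent, because the start of a second subsequent therapy counts for some patients and is set aside for others according to later follow-up. For the patients concerned PFS2 can only be lengthened, by the interval from the switch to the later progression. The conclusion rests on applying the steps as worded and on later-line progressions being available to the derivation, which protocol 1.2 supports and protocol 5.6.2 leaves less clear.

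A reader might go further and infer that the PFS2 hazard ratio is biased. The documents give no switching rate, no difference between arms and no direction, so they support only that it can be biased if switching without documented progression differs by arm. Nor is there any effect on the main claims: PFS2 is outside the six hypotheses (ORR, OS and PFS, each in two populations) covered by the error control in SAP 15.3. The matter is minor but clear.

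**What to change.** In SAP 7.5.4.1, for patients with subsequent therapy, replace the first two steps by one: the event date is the earliest of the first investigator-assessed progression after the start of the first subsequent therapy, the start of the second subsequent therapy, and death. Otherwise censor at the last known alive date. Limiting the first step to the first progression on or before the start of the second subsequent therapy gives the same dates.

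Rewording the steps alone would leave them at odds with the definitions. SAP 4.3, the opening of SAP 7.5.4.1 and protocol 9.5 should therefore also name the start of a second subsequent therapy as an event.

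The cost is a few lines of text and a small programming change. No new data are needed, since protocol 5.6.2 already has the line of therapy, the start date of each regimen and progression after the next line collected.

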7.5.4.2 Concordance Between BICR and Investigator Assessment of Progression

For the purpose of assessing concordance between the BICR and investigator tumor assessments, progression status will be categorized as documented progression, death or censored. A cross tabulation between the BICR and the investigator progression status will be presented, by treatment group. The primary analysis of PFS (ITT I/P-risk population and ITT all-risk population) will be used for this assessment.

A by patient listing of BICR and investigator PFS status and the time between progression dates according to the BICR and the investigator will be provided.

7.5.4.3 Duration of Response

Analysis of duration of response (DOR) will be performed for responders (confirmed CR or PR) only. Duration of Response (DOR) is defined as the time between the date of first confirmed documented response (CR or PR) to the date of the first documented tumor progression as determined by the BICR per mRECIST 1.1, or death due to any cause, whichever occurs first. Patients who start subsequent anti-cancer therapy without a prior reported progression will be censored at the last evaluable tumor assessments prior to initiation of the subsequent anticancer therapy. Patients who die without a reported prior progression will be considered to have progressed on the date of their death. For patients who neither progress nor die, DOR will be censored on the date of their last evaluable tumor assessment. The DOR for each treatment group will be estimated using the Kaplan-Meier method. Median values of DOR with corresponding 95% CI for each treatment group will be computed based on a log-log transformation method.

7.5.4.4 Time to Response

A descriptive analysis of time to response (TTR) will be performed for responders (confirmed CR or PR) only. Time to response is defined as the time from the date of randomization to date of first documented CR or PR per mRECIST 1.1 as assessed by BICR. TTR will be summarized using descriptive statistics only (median, min, max). TTR per investigator's assessment will be summarized similarly.

7.5.4.5 Clinical Benefit Rate

The CBR per both BICR and investigator's assessment, and its corresponding 95% exact CI will be calculated by the Clopper and Pearson method for each treatment arm.

7.5.5 Subgroup Analyses

The following subgroup analyses will be performed for ORR by BICR, OS, and PFS by BICR.

The benefit of NKTR-214 in combination with nivolumab compared to TKI will be evaluated by a unstratified rate difference for ORR by BICR or unstratified hazard ratio for OS and PFS by BICR with its 95% CI based on a Cox regression model for each subgroup. The hazard ratios and their 95% CI will be displayed in a forest plot. Subgroup analyses may not be performed if the sample size is too small to provide accurate estimates. The following subgroup analyses (except age, race, region, and sex) will be conducted if the number of patients in each subgroup is > 10 for each treatment group.

- IMDC prognostic score (0 [favorable risk], 1-2 [intermediate risk], 3-6 [poor risk])
- Baseline PD-L1 status ($\geq 1\%$, $<1\%$, indeterminant or non-evaluable)
- Age categorization (< 65 , ≥ 65 years)
- Sex (male, female)
- Race (White, Black, Asian, Other)
- Geographic region (US, Rest of the world)
- Baseline Karnofsky performance status (<80 , ≥ 80)
- Sarcomatoid histology (Yes vs No)
- Prior nephrectomy (Yes, No)
- Baseline bone mets as per BICR (Yes, No)

The following subgroups may be explored:

- TKI choice (sunitinib, cabozantinib)
- Baseline PD-L1 status ($\geq 5\%$, $<5\%$, indeterminant or non-evaluable; $\geq 10\%$, $< 10\%$, indeterminant or non-evaluable)
- Time from initial RCC diagnosis to randomization (≤ 1 year, > 1 year)
- Patients with history of brain metastases (Yes, No)
- Prior radiotherapy (Yes, No)
- Baseline LDH level (≤ 1.5 x ULN, > 1.5 x ULN)
- Baseline Hemoglobin ($<LLN$, $\geq LLN$)

- Baseline Corrected Calcium (\leq ULN, $>$ ULN)
- Baseline Absolute Neutrophil Count (\leq ULN, $>$ ULN)
- Baseline Platelet Count (\leq ULN, $>$ ULN)
- Baseline Alkaline phosphatase (\leq ULN, $>$ ULN)
- Tumor burden at baseline per BICR and per investigator (\leq 1st Tertile, $>$ 1st Tertile to \leq 2nd Tertile, $>$ 2nd Tertile).
- Baseline liver mets as per BICR (Yes, No)
- Baseline lung mets as per BICR (Yes, No)
- Baseline lymph node mets as per BICR (Yes, No)

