5.10 Biomarkers

A variety of factors that could potentially predict clinical responses to NKTR-214 combined with nivolumab or to TKIs will be investigated in peripheral blood and in tumor specimens taken from all patients prior to, and on treatment and as outlined in Table 6 and the Schedule of Events (Table 1 through Table 4), respectively. Data from these investigations will be evaluated for associations with response, survival (OS, PFS), and/or safety (AE) if data allows. [REDACTED]

[REDACTED]

Complete instructions on the collection, processing, handling and shipment of all samples described herein will be provided in the Laboratory Manual.

Sites may only opt out of biomarker sampling if they meet one of the following criteria: inability to process these samples, insufficient storage facilities, or unavailable courier pickup / dry ice.

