3.2 Secondary Objectives

The key secondary objectives are:

- To compare the progression-free survival (PFS) by BICR using mRECIST 1.1 of NKTR-214 combined with nivolumab to TKI monotherapy (sunitinib or cabozantinib) in IMDC intermediate- or poor- patients with previously untreated advanced RCC
- To compare the PFS by BICR using mRECIST 1.1 of NKTR-214 combined with nivolumab to TKI monotherapy (sunitinib or cabozantinib) in IMDC all-risk patients with previously untreated advanced RCC

The other secondary objectives are:

- To estimate the incidence of adverse events (AEs) of NKTR-214 combined with nivolumab versus TKI monotherapy (sunitinib or cabozantinib) in patients with previously untreated advanced RCC
- To evaluate whether programmed cell death ligand 1 (PD-L1) expression (< 1% vs \geq 1%) using the PD-L1 immunohistochemistry (IHC) 28-8 pharmDx assay is a predictive biomarker for ORR, PFS, and OS in patients with previously untreated advanced RCC
- To characterize changes in cancer-related symptoms and quality-of-life in patients with previously untreated advanced RCC using the National Comprehensive Cancer Network/Functional Assessment of Cancer Therapy (NCCN/FACT) Symptom Index for Kidney Cancer (FKSI-19)

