The minimum and maximum number of OS events in IMDC intermediate- or poor-risk population for the final analysis are 200 and 308, respectively. The minimum event size is calculated to achieve 90% power with $\alpha=0.049$ (two-sided) assuming an exponential distribution in each treatment arm and a HR = 0.63 with median OS for the TKI arm of 26 months in IMDC intermediate- or poor- risk population. The maximum event size is determined based on the minimum clinically meaningful effect. When the minimum event size of 200 is reached in the IMDC intermediate- or poor-risk population, approximately 211 events are expected to be observed in the IMDC all-risk population, which gives approximately 80% power with $\alpha=0.049$ (two-sided) assuming an exponential distribution in each treatment arm and a HR = 0.68 with median OS for the TKI arm of 32.9 months in the IMDC all-risk population.

The detailed sample size adaptation rules based on conditional power will be described in an appendix of the DMC Charter, which will not be accessible to the study team or sites to prevent introduction of any potential bias; however, the operational procedures will be described in the

DMC charter, which is accessible to the study team. The key secondary endpoint of PFS in the IMDC intermediate- or poor-risk population and the IMDC all-risk population will be tested hierarchically given the statistical significance of OS.

Figure 2 provides the study flow and decision-making time points.

Figure 2: Study Flow and Decision-Making Time Points

IA=interim analysis, FA=final analysis, I/P-risk=IMDC intermediate or poor risk, All-risk=IMDC all risk
 a. The timeline for IA is based on accrual and the OS assumptions and will be triggered based on the number of OS events in I/P-risk population.
 b. The timeline for FA will be triggered based on the number of OS events in I/P-risk or all-risk population.

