 - Changes from baseline will be compared between treatment groups using a linear mixed model with repeated measures (MMRM) with treatment, time, treatment and time interaction, baseline score, and stratification variables as covariates. An unstructured covariance matrix will be used unless the model fails to converge. Treatment effect on the change from baseline will be compared by the difference in the least-square means and corresponding 95% CI. The MMRM assumes that the missing data mechanism is ignorable (i.e., missing at random).

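### The secondary objective asks whether PD-L1 is predictive, but the visible SAP plans only separate subgroup estimates, with no treatment-by-PD-L1 contrast and no stated basis for judging the objective

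*SAP*

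**What the plan says.** Among the other secondary objectives in Protocol 3.2 and SAP 3.2 is to evaluate whether PD-L1 expression, cut at 1%, "is a predictive biomarker for ORR, PFS, and OS in patients with previously untreated advanced RCC".

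The only visible section that compares the arms on efficacy by PD-L1 level is SAP 7.5.5. It covers ORR, OS and PFS. The treatment benefit "will be evaluated by a unstratified rate difference for ORR by BICR", or by an "unstratified hazard ratio for OS and PFS by BICR with its 95% CI based on a Cox regression model for each subgroup". For presentation, "The hazard ratios and their 95% CI will be displayed in a forest plot". The 1% cut-point is in the planned list of subgroups; the 5% and 10% cut-points are in the list that may be explored. PD-L1 is not exempt from the size conditions: each subgroup needs more than 10 patients per arm, and "Subgroup analyses may not be performed if the sample size is too small to provide accurate estimates".

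Section 7.5.5 contains no treatment-by-PD-L1 term, ratio of hazard ratios or difference between rate differences. It gives no criterion for calling PD-L1 predictive. The one interaction in a visible SAP model is in the FKSI-19 repeated-measures model (SAP 7.6.1), fitted "with treatment, time, treatment and time interaction, baseline score, and stratification variables as covariates". The readable part of Protocol 5.10 says: "Data from these investigations will be evaluated for associations with response, survival (OS, PFS), and/or safety (AE) if data allows".

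**The concern.** A marker is predictive when the treatment effect differs between its levels. The quantity that answers the objective is therefore a between-level contrast of treatment effects. Two within-level effects shown side by side are its ingredients. An association between marker and outcome, as in Protocol 5.10, does not separate a prognostic marker from a predictive one.

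Without a planned contrast, the objective is likely to be judged by eye, typically by whether one interval excludes the null and the other does not. The PD-L1 >=1% group is expected to be much the smaller, so its interval is wider and such a split is common even when the effects are identical. At stake is how a stated secondary objective is reported. No primary or key secondary test depends on it.

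**Working it through.** **Inputs**
- OS events at the final analysis, intermediate/poor-risk population: 200 minimum, 308 maximum. Design HR 0.63, two-sided alpha 0.049, 90% power (SAP 6.2.2). Allocation 1:1 (SAP 5.1).
- PD-L1 >=1% in the cited Phase 3 trial of nivolumab plus ipilimumab versus sunitinib (Protocol 2.3.1): 100 of 384 (26%) and 114 of 392 (29%). These are shares of patients, not of events.
- Assumption: 27% of OS events are PD-L1 >=1%, range 20% to 35%, and all events come from PD-L1-evaluable patients.

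**1. The plan's own figure.** Schoenfeld: d = 4(1.9685 + 1.2816)² / (ln 0.63)² = 42.25 / 0.2135 = 198, against the stated 200. It reproduces, so 200 is a fair measure of the information available.

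**2. Discordant intervals with no predictive effect.** Take HR 0.63 in both PD-L1 groups. With variance 4/events for the log HR, the chance that a 95% CI excludes 1 is Φ(√(events/4) × 0.462 − 1.96).
- 200 events, 54 and 146 by group: 0.397 and 0.797. Exactly one excludes 1: 0.397 × 0.203 + 0.797 × 0.603 = 0.56.
- 308 events, 83.2 and 224.8 by group: 0.558 and 0.934. Exactly one: 0.558 × 0.066 + 0.934 × 0.442 = 0.45.

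| Share of events PD-L1 >=1% | 200 events | 308 events |
|---|---|---|
| 20% | 0.627 | 0.553 |
| 27% | 0.56 | 0.45 |
| 35% | 0.505 | 0.363 |

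**3. What the contrast adds, using the cited trial.** Standard errors are taken from the reported CIs as ln(upper/lower)/3.92; log HRs subtract and variances add.
- OS: HR 0.45 (0.29 to 0.71) for >=1% and 0.73 (0.56 to 0.96) for <1%. SEs 0.228 and 0.138, combined 0.267. Ratio 0.62 (95% CI 0.37 to 1.04), p = 0.07.
- PFS: HR 0.46 (0.31 to 0.67) and 1.00 (0.80 to 1.26). SEs 0.197 and 0.116, combined 0.228. Ratio 0.46 (0.29 to 0.72), p = 0.0007.

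Both OS intervals exclude 1 and the point estimates look far apart, yet the evidence that they differ is inconclusive. For PFS it is strong. The contrast shows this directly.

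**4. Precision of the contrast in this trial.** SE of the log ratio = √(4/54 + 4/146) = 0.32 at 200 events and √(4/83.2 + 4/224.8) = 0.26 at 308. Power for a ratio of 0.616 (0.45/0.73), with |ln 0.616| = 0.484:
- 200 events: Φ(0.484/0.3185 − 1.96) = 33% (28% to 37% over the range of shares)
- 308 events: Φ(0.484/0.2567 − 1.96) = 47% (40% to 53%)

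For ORR, take 500 patients, the same 27% (67.5 and 182.5 per arm by group) and the planned rates of 27% and 45%. The SE of the difference between rate differences is √[(0.1971 + 0.2475)(1/67.5 + 1/182.5)] = 0.095, a 95% half-width of about 19 percentage points.

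**The case against.** Four objections carry weight.

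**The information is already planned.** A reader might infer that the objective has no analysis, or that the planned output cannot answer it. The documents do not support that. PD-L1 at 1% is a planned subgroup for all three endpoints. The two groups are disjoint, so a ratio of hazard ratios follows from the reported intervals, exactly as in step 3. What is missing is the prespecified contrast and the basis for judging it. The size condition is also unlikely to bite: 27% of 500 is about 135 patients.

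**The SAP states no significance rule for subgroups.** A reader might take the 56% as an error rate of the planned analysis. It is not. SAP 7.5.5 plans estimates, intervals and a forest plot, and nowhere says that PD-L1 is predictive if one interval excludes 1. The figure describes an informal reading that the plan leaves open.

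**Redaction.** Text in Protocol 5.10 and between 9.7 and 9.9, and heading words in SAP 12, are blacked out. A treatment-by-PD-L1 analysis there cannot be excluded, so the point holds for the visible text only.

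**The contrast has low power, and its event share is assumed.** Both are true. The cited trial reports shares of patients. Its sunitinib arm had lower 18-month survival with PD-L1 >=1% (53% against 64%), so the event share need not equal prevalence; hence the range. Low power argues for reporting an estimate with its interval. It does not argue for relying on two separate intervals, which support a predictive claim no better.

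**Conclusion.** The point holds in limited form. The visible plan poses a question about a difference in treatment effects, estimates the effects separately, and does not say how the question will be decided. If the intervals were compared informally, they would disagree on excluding 1 about 56% of the time at 200 events (roughly 50% to 63%) and 45% at 308 (36% to 55%) when PD-L1 has no predictive effect. This assumes a common HR of 0.63, independent groups, the normal approximation, and 20% to 35% of events in PD-L1 >=1%. The objective is outside the alpha-controlled hierarchy, so no primary or key secondary conclusion changes. The change should be made because it is cheap and gives a stated objective a defined answer.

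**What to change.** In SAP 7.5.5, for PD-L1 >=1% vs <1%, add:
- **OS and PFS:** the ratio of hazard ratios with 95% CI from a Cox model with treatment, PD-L1 and their interaction, stratified by IMDC score and TKI choice. State that the PFS ratio is an average effect if hazards are non-proportional, which SAP 7.5.2.1 anticipates.
- **ORR:** the difference between the two subgroup rate differences with 95% CI. This keeps the SAP's own scale; a logistic interaction would not, because interaction depends on the scale.
- **Reporting:** label these as exploratory estimates, give them in both the intermediate/poor-risk and all-risk populations, and exclude indeterminate or non-evaluable samples from the contrast.
- **Conclusion:** base any statement that PD-L1 is predictive on the contrast and its interval, not on the separate subgroup intervals.

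The cost is a few lines of text and a small set of extra outputs from data already collected. The stratified ratio will not exactly equal the quotient of the unstratified HRs in the forest plot, so a footnote should say so. The main drawback is imprecision: the SAP should state that a non-significant contrast is not evidence that PD-L1 has no predictive effect.
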